2. STUDY OBJECTIVES AND ENDPOINTS

Primary Objective:	Primary Endpoints:
To compare the pharmacokinetics of PF-05221304 (both total and unbound) following administration of a single oral dose in adult subjects with varying degrees of hepatic impairment relative to age- and body weight-matched subjects without hepatic impairment.	PF-05221304 PK parameters derived from plasma: 
 C_{max}, AUC_{inf}, f_u, $C_{max,u}$, and $AUC_{inf,u}$.
Secondary Objectives:	Secondary Endpoints:
To compare additional pharmacokinetic parameters (both total and unbound) of PF-05221304 following administration of a single oral dose in adult subjects with varying degrees of hepatic impairment relative to age- and body weight-matched subjects without hepatic impairment.	PF-05221304 PK parameters derived from plasma: 
 T_{max}, AUC_{last}, $AUC_{last,u}$, CL/F, CL_u/F, V_z/F, $V_{z,u}/F$ and $t_{1/2}$, as data permit.
To evaluate the safety and tolerability of a single oral dose of PF-05221304 when administered to adult subjects with varying degrees of hepatic impairment relative to age- and body weight-matched subjects without hepatic impairment.	Assessment of treatment-emergent adverse events, clinical laboratory tests, vital signs, and 12-lead ECGs.

090177e190d319bb\Approved\Approved On: 29-Apr-2019 07:31 (GMT)

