5.5. Administration

Administration of investigational product (PF-05221304), will occur at 8:30 AM (\pm 1 hour) with the morning meal – refer to [Section 4.4.1](#). A single, oral, 25 mg dose of PF-05221304 will be administered. Subjects will swallow the investigational product whole, and will not manipulate or chew the investigational product prior to swallowing. Investigator site personnel will administer investigational product to subjects with ambient temperature water of approximately 120 mL.

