9.3.3. Statistical Methods

The effect of varying degrees of hepatic impairment on PK parameters will be assessed by constructing 90% confidence intervals around the estimated difference between each of the Test (impaired) cohorts and the Reference (without hepatic impairment) cohort using a one-way ANOVA model based on natural log transformed data.

One-way analysis of variance (ANOVA) will be used to compare the natural log transformed PF-05221304 AUC_{inf} , AUC_{last} and C_{max} , unbound AUC_{inf} ($AUC_{inf,u}$), unbound AUC_{last} ($AUC_{last,u}$), and unbound C_{max} ($C_{max,u}$), as data permit, for each of the hepatic impairment classification cohorts (Test) to the cohort without hepatic impairment (Reference). Estimates of the adjusted mean differences (Test-Reference) and corresponding 90% confidence intervals will be obtained from the model. The adjusted mean differences and 90% confidence intervals for the differences will be exponentiated to provide estimates of the ratio of adjusted geometric means (Test/Reference) and 90% confidence intervals for the ratios.

CCI

[figure not shown]
The PF-05221304 PK parameters C_{max} , AUC_{last} , AUC_{inf} , f_u , T_{max} , $t_{1/2}$, CL/F , V_z/F , $AUC_{inf,u}$, $AUC_{last,u}$, $C_{max,u}$, CL_u/F , and V_{zu}/F will be summarized descriptively by hepatic function cohort. Individual PF-05221304 concentrations will be listed and summarized descriptively by nominal PK sampling time and hepatic function cohort. Individual subject and summary profiles (median and means) of the concentration-time data will be plotted by treatment for both total plasma PF-05221304 and unbound PF-05221304. For summary statistics and summary plots by sampling time, the nominal PK sampling time will be used; for individual subject plots by time, the actual PK sampling time will be used. PF-05221304 AUC_{inf} , AUC_{last} , C_{max} , $AUC_{inf,u}$, $AUC_{last,u}$, and $C_{max,u}$ individual subject parameters will be plotted by hepatic function cohort.

Linear regression may be used to analyze the potential relationship between appropriate PK parameters (eg CL/F and V_z/F) and hepatic function (eg, serum albumin concentration, or prothrombin time). Estimates of the slope and intercept, together with their precision (90% confidence interval [CI]), and the coefficient of determination will be obtained from the model.

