6.3. Other Endpoints

6.3.1. PK Endpoints

Blood samples for PK analysis of PF-05221304 will be taken according to the Schedule of Activities given in the protocol.

The following PK parameters will be calculated for PF-05221304 (if possible) from the concentration-time data using standard non-compartmental methods:

Table 3. Noncompartmental PK Parameters

PK Parameter	Analysis Scale	PF-05221304	Definition
AUC_{last}	ln	A, D	Area under the plasma concentration-time profile from time zero to the time of the last quantifiable concentration (C_{last})
$AUC_{last,u}$	ln	A, D	Unbound area under the plasma concentration-time profile from time zero to the time of the last quantifiable concentration (C_{last})
AUC_{inf}^*	ln	A, D	Area under the plasma concentration-time profile from time zero extrapolated to infinite time
$AUC_{inf,u}^*$	ln	A, D	Unbound area under the plasma concentration-time profile from time zero extrapolated to infinite time
C_{max}	ln	A, D	Maximum plasma concentration
$C_{max,u}$	ln	A, D	Unbound maximum plasma concentration
T_{max}	R	D	Time for C_{max}
$t_{1/2}^*$	R	D	Terminal half-life
CL/F^*	ln	A, D	Apparent clearance
CL_u/F^*	ln	A, D	Unbound apparent clearance
V_z/F^*	ln	A, D	Apparent volume of distribution
V_{z_u}/F^*	ln	A, D	Unbound apparent volume of distribution
Fu^+	R	D	Fraction unbound

Key: A=analyzed using statistical model, D=displayed with descriptive statistics,
ln=natural-log transformed, R=raw (untransformed), *=if data permits; u=unbound fraction
+ = Reported in eNCA as protein free fraction.

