8. STATISTICAL METHODOLOGY AND STATISTICAL ANALYSES

8.1. Statistical Methods

The effect of the hepatic impairment on PK parameters will be assessed by constructing 90% confidence intervals around the estimated difference between each of the Test (impaired cohorts) and the Reference (normal hepatic function cohort) using a one-way ANOVA model based on natural log transformed data.

The relationship between PK parameters and hepatic function will be determined by a linear regression model.

CCI

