8.2. Statistical Analyses of PK Parameters

One-way analysis of variance (ANOVA) will be used to compare the natural log transformed PF-05221304 AUC_{inf} , AUC_{last} and C_{max} , unbound AUC_{inf} ($AUC_{inf,u}$), unbound AUC_{last} ($AUC_{last,u}$), and unbound C_{max} ($C_{max,u}$), as data permit, for each of the hepatic impairment classification cohorts (Test) to the cohort without hepatic impairment (Reference). Estimates of the adjusted mean and corresponding 90% confidence intervals will be obtained from the model for each cohort. Estimates of the adjusted mean differences (Test-Reference) and corresponding 90% confidence intervals will be obtained from the model as well. The adjusted mean estimates and adjusted mean differences and 90% confidence intervals for the estimates and differences will be exponentiated to provide estimates of adjusted geometric means and estimates of the ratio of adjusted geometric means (Test/Reference) and 90% confidence intervals for the estimates and for the ratios respectively (see Appendix 1 for SAS code).

Additionally, as an exploratory analysis, age, body weight, and gender (see Section 6.4) will be explored as a covariate/factor in the ANOVA/ANCOVA model, as appropriate (see Appendix 1 for SAS code).

Linear regression may be used to analyze the potential relationship between the following PK parameters -AUC_{inf}, and CL/F separately - and the following hepatic function - serum albumin, prothrombin time, and total bilirubin separately -. Estimates of the slope and intercept, together with their precision (90% confidence interval [CI]), and the coefficient of determination (ie R-squared and adj-R-squared) will be obtained from the model.

Plots of PK parameters -AUC_{inf}, and CL/F separately - versus hepatic function - serum albumin, prothrombin time, total bilirubin separately - will be constructed. A regression line and 90% confidence region for the PK parameters and hepatic function will be included. (See appendix 1 for example of SAS code to produce the figure).

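### The SAP's liver-function regressions use only AUCinf and CL/F, which mirror each other on the ln scale at one fixed dose; swap one for AUCinf,u

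*SAP*

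**What the plan says.** On the regression, SAP 8.2 states "Linear regression may be used to analyze the potential relationship between the following PK parameters". The parameters it names are AUCinf and CL/F, each taken separately against "serum albumin, prothrombin time, and total bilirubin separately". Plots of the same pairs, with a regression line and a 90% confidence region, are stated as a commitment. SAP 8.1 is also firmer than 8.2: "The relationship between PK parameters and hepatic function will be determined by a linear regression model". The visible regression text gives no analysis scale.

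SAP Table 3 enters both AUCinf and CL/F as ln-transformed with flag A, under the legend "Key: A=analyzed using statistical model, D=displayed with descriptive statistics".

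Protocol 9.3.3 has the parallel sentence, "Linear regression may be used to analyze the potential relationship between appropriate PK parameters", with CL/F and Vz/F as its examples. AUCinf is not among them. The SAP put AUCinf where the protocol had Vz/F.

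On dose, protocol 5.5 says "A single, oral, 25 mg dose of PF-05221304 will be administered". Protocol Table 5 defines CL/F as Dose/AUCinf, AUCinf,u as f_u × AUCinf, and CLu/F as f_u × CL/F. The primary objective (protocol Section 2) is "To compare the pharmacokinetics of PF-05221304 (both total and unbound) following administration of a single oral dose".

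**The concern.** There are two separate problems. First, when every subject has the same dose, CL/F is a constant divided by AUCinf. Regressing both on the same marker gives the same information twice on the ln scale, or two incompatible straight lines on the raw scale.

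Second, both outcomes are total drug. Total clearance depends on both the free fraction and the unbound clearance. If f_u rises as liver function worsens, that rise offsets a fall in unbound clearance, and the regressions on albumin, prothrombin time and bilirubin could look flat. At stake is how unbound clearance relates to individual liver markers. That matters for a drug whose main clearance is predicted (protocol 1.3) to be active uptake into the liver.

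**Working it through.** **The plan's own figure.** The documents state no figure for the regression. The only computed figure is protocol Table 4 on precision, and it reproduces with half-width h = t(0.95, 10) × SD × √(2/6) × √(χ²(0.80, 10)/10). At SD 0.23, h = 1.812 × 0.23 × 0.577 × 1.159 = 0.279. Precision is then 1 − e^(−0.279) = 24.3% and the interval is 2e^(±0.279) = 1.513 to 2.644, against the printed 24% (1.51; 2.64). The other two columns also match: 17.6% (1.647; 2.428) and 28.8% (1.424; 2.809). Here it only supplies a plausible ln-scale SD.

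**Count.** 2 outcomes × 3 markers = 6 regressions.

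**ln scale.** CL/F = 25/AUCinf gives ln(CL/F) = ln(25) − ln(AUCinf). A slope b for ln AUCinf becomes −b for ln CL/F, every residual changes sign, and R-squared is unchanged. One simulated set of 24 subjects at SD 0.23 confirms it: slope −0.4814 (90% CI −0.609 to −0.354) against +0.4814 (0.354 to 0.609), with R-squared 0.6562 for both. Only 3 of the 6 are distinct.

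**Raw scale.** If AUCinf = a + b × marker with b not zero, then CL/F = 25/(a + b × marker), which is a curve. In simulation the raw values correlate at about −0.89 to −0.94 and the two R-squared values differ by 0.05 to 0.07 on average. They are not duplicates, but a straight line cannot be right for both.

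**Unbound outcome.** From Table 5, Dose/AUCinf,u = Dose/(f_u × AUCinf) = (CL/F)/f_u. Write this unbound clearance as CL*. Then CL/F = f_u × CL*, and for impaired/normal ratios:

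- AUCinf ratio = 1/(f_u ratio × CL* ratio)
- AUCinf,u ratio = 1/(CL* ratio)
- Table 5 CLu/F ratio = (f_u ratio)² × CL* ratio

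The f_u and CL* ratios below are assumptions.

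| f_u ratio | CL* ratio | AUCinf | AUCinf,u | CLu/F per Table 5 |
|---|---|---|---|---|
| 1 | 0.5 | 2.00 | 2.00 | 0.50 |
| 1.25 | 0.5 | 1.60 | 2.00 | 0.78 |
| 1.5 | 0.5 | 1.33 | 2.00 | 1.125 |
| 1.5 | 0.67 | 1.00 | 1.49 | 1.51 |
| 2 | 0.5 | 1.00 | 2.00 | 2.00 |
| 2.5 | 0.4 | 1.00 | 2.50 | 2.50 |

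**Effect on slopes.** On the ln scale slopes add. Assume ln CL* has slope 0.40 per g/dL of albumin, and ln f_u has slope 0, −0.2 or −0.4:

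- CL/F: 0.40 + 0 = 0.40; 0.40 − 0.2 = 0.20; 0.40 − 0.4 = 0.00
- Dose/AUCinf,u: 0.40 in all three cases
- Table 5 CLu/F: 0.40 + 2 × (0, −0.2, −0.4) = 0.40, 0.00, −0.40

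**Chance of seeing it.** Simulated trials of 24 subjects, ln SD 0.23, assumed albumin values and severe/normal ratios, CL* ratio 0.5 throughout:

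| f_u ratio | ln AUCinf slope (90% CI excludes 0) | ln AUCinf,u slope (90% CI excludes 0) |
|---|---|---|
| 1 | −0.36 (100%) | −0.36 (100%) |
| 1.5 | −0.15 (69%) | −0.36 (100%) |
| 2 | 0.00 (10%) | −0.36 (100%) |

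The 10% is the rate expected of a 90% interval when there is no relation at all.

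**The case against.** The strongest reply is that unbound exposure is already covered where it counts. The main analysis, "One-way analysis of variance (ANOVA) will be used to compare the natural log transformed PF-05221304", includes AUCinf,u, AUClast,u and Cmax,u with 90% confidence intervals. Box plots show the same parameters, and f_u is summarised by cohort. A reader might infer that the study could miss a loss of unbound clearance. The documents do not support that: the loss would show by cohort, and only its relation to the individual markers could be lost.

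The regression is supportive and, in SAP 8.2 and protocol 9.3.3, optional. SAP 4.1 and 4.2 plan no hypothesis tests or decision rules, so duplicates cost no error rate. A reader might also infer that dosing recommendations would rest on these regressions, but protocol 1.4 refers to the data of the study as a whole. All of this stands and limits the consequence. It does not make a repeated regression informative, and the plots are a firm commitment.

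On scale, the visible regression text is silent, parts of SAP Appendix 1 are redacted and might state it, and SAP 8.2 allows alternative transformations after residual checks. So exact duplication holds only on the ln scale. That reading is well supported: CL/F is flagged A on the ln scale in Table 3 and is absent from the ANOVA list, which leaves the regression as the only visible model the entry can describe.

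Finally, nothing readable says that low albumin raises f_u for this drug. Protocol 1.3.2 plans to measure f_u in each subject to find out. It would be wrong to say that masking will occur. Nor is the change from Vz/F to AUCinf a breach: the protocol's regression list is by example, and protocol Section 9 lets the SAP modify the plan.

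**Conclusion.** The point holds as a limited one. On the ln scale of SAP Table 3, three of the six regressions repeat the other three exactly; this is algebra and needs no assumption beyond the scale. On the raw scale they differ, but one straight-line model cannot suit both outcomes.

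The missing unbound outcome is a real gap in these supportive regressions and plots, given objectives that cover total and unbound drug. Its size cannot be fixed from the documents. It runs from no masking (f_u unchanged), through partial masking (a 2-fold rise in unbound AUC seen as 1.60-fold or 1.33-fold in total AUC), to complete masking when the f_u and unbound clearance ratios multiply to 1. The simulated percentages rest on assumed albumin, f_u and clearance values and illustrate the mechanism only.

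The obvious substitute, CLu/F, is not safe as defined. Table 5's f_u × CL/F is not Dose/AUCinf,u, and it can show clearance doubling when unbound clearance has halved.

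**What to change.** In SAP 8.2, for both the regressions and the plots:

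- Keep one of AUCinf or CL/F and replace the other with AUCinf,u (equivalently Dose/AUCinf,u on the ln scale, with the slope sign reversed) for each of the three markers.
- State that the outcomes are analysed on the ln scale, as in Table 3.
- Do not use CLu/F until its definition in protocol Table 5 is reconciled with AUCinf,u = f_u × AUCinf.
- Make SAP 8.1 and 8.2 agree on whether the regression is planned or optional, and record why Vz/F was dropped.

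The cost is one swapped variable in existing code and a few lines of text. There are still six regressions, now all distinct, and no new data are needed because f_u is already measured in every subject.

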8.3. Safety Analysis

A set of summary tables split by hepatic function cohort will be produced to evaluate any potential risk associated with the safety and toleration of administering PF-05221304.

8.3.1. Treatment and Disposition of Subjects

Subject evaluation groups will show end of study subject disposition and will show which subjects were analyzed for pharmacokinetics, pharmacodynamics (CP-I and CP-III), as well as for safety (adverse events and laboratory data). Frequency counts will be supplied for subject discontinuation(s) by hepatic function cohort.

Data will be reported in accordance with the sponsor reporting standards.

8.3.2. Demographic and Clinical Examination Data

A breakdown of demographic data will be provided for age, race, weight, body mass index, and height. Each will be summarized by sex at birth and 'All Subjects' in accordance with the sponsor reporting standards.

8.3.3. Discontinuation(s)

Subject discontinuations, temporary discontinuations due to adverse events will be detailed and summarized by hepatic function cohort.

Data will be reported in accordance with the sponsor reporting standards.

8.3.4. Adverse Events

Adverse events will be reported in accordance with the sponsor reporting standards by hepatic function cohort.

8.3.5. Laboratory Data

Laboratory data will be listed in accordance with the sponsor reporting standards.

8.3.6. Vital Signs Data

The baseline measurement is the last predose measurement.

For each planned timepoint, baseline values and change from baseline values within each hepatic function cohort will be summarized with descriptive statistics (using sponsor default standards).

These data will be listed in accordance with the sponsor reporting standards.

8.3.7. ECG Data

The baseline measurement is the predose measurement.

For each planned timepoint, baseline values and change from baseline values within each hepatic function cohort will be summarized with descriptive statistics (using sponsor default standards).

These data will be listed in accordance with the sponsor reporting standards.

8.3.8. Other Safety Data

None.

8.3.9. Concomitant Treatments

All concomitant medication(s) as well as non-drug treatment(s) will be provided in the listings.

8.3.10. Screening and Other Special Purpose Data

Prior medication(s) and non-drug treatment(s), serum FSH concentrations (in females), and serum β -hCG (in females), obtained at Screening, will be databased.

CCI

090177e190d319bc\Approved\Approved On: 29-Apr-2019 07:33 (GMT)

10. APPENDICES

Appendix 1. SAS CODE FOR ANALYSES

/* Letter assignments for cohort within the estimate statement in the code below are as follows;

A = Severe (Test)
 B = Moderate (Test)
 C = Mild (Test)
 D = Normal (Reference);
 */;

For ANOVA: An example of the PROC GLM code is provided below:

```
proc glm data=tab.pk;
  class cohort;
  model l&var = cohort / ss3 clparm alpha=0.1;
  lsmeans cohort;
  estimate 'Severe vs Normal'      cohort 1 0 0 -1;
  estimate 'Moderate vs Normal'    cohort 0 1 0 -1;
  estimate 'Mild vs Normal'        cohort 0 0 1 -1;
  ods output Estimates = est&var;
  ods output FitStatistics = fit&var;
  ods output ModelANOVA = tst&var;
  ods output OverallANOVA = overall&var;
run;
```

[figure not shown]
For ANCOVA: An example of the PROC GLM code is provided below:

```
proc glm data=tab.pk;
  class cohort;
  model l&var = cohort age weight / ss3 clparm alpha=0.1;
  lsmeans cohort;
  estimate 'Severe vs Normal'      cohort 1 0 0 -1;
  estimate 'Moderate vs Normal'    cohort 0 1 0 -1;
  estimate 'Mild vs Normal'        cohort 0 0 1 -1;
  ods output Estimates = est&var;
  ods output FitStatistics = fit&var;
  ods output ModelANOVA = tst&var;
  ods output OverallANOVA = overall&var;
run;
```

CCI

090177e190d319bc\Approved\Approved On: 29-Apr-2019 07:33 (GMT)

090177e190d319bc\Approved\Approved On: 29-Apr-2019 07:33 (GMT)

CCI

090177e190d319bc\Approved\Approved On: 29-Apr-2019 07:33 (GMT)
